### 2.2. MTD Determination (Part 1)

A modified toxicity probability interval method (mTPI) targeting a DLT rate of 25% with an equivalence interval (20%-30%) will be utilized in order to estimate MTD. Patients will be enrolled in cohorts of 2 to 4, starting with 0.015 mg/kg for the first cohort. Subsequent dose levels may include a maximum 100% escalation until either the dose is  $\geq 0.060$  mg/kg, a patient experiences a DLT or Grade 2 thrombocytopenia considered related to PF-06647263

after which, dose escalation in subsequent cohorts will follow a modified Fibonacci scheme with maximum dose increases of 67%, 50%, 33%, 33%. Table 1 illustrates the possible dose levels when the Modified Fibonacci scheme is initiated at the 3rd dose level. Intermediate dose levels to further evaluate the safety and/or PK may be evaluated following discussion between Sponsor and Investigator.

	Modified Fibonacci^ scheme starts from dose level 3	Modified Fibonacci^ scheme starts from dose level 2	Modified Fibonacci^ scheme starts from dose level 1
Dose Level	Dose (mg/kg Q3W)	Dose (mg/kg Q3W)	Dose (mg/kg Q3W)
-1	0.01	0.01	0.01
1 (Starting dose)	0.015	0.015	0.015
2	0.030	0.030	0.025
3	0.060	0.050	0.038
4	0.100	0.075	0.050
5	0.150	0.100	0.067
6	0.200	0.134	0.089
7	0.267	0.178	0.119
8		0.238	0.158
9			0.211

The modified toxicity probability interval (mTPI) design uses a Bayesian decision-theoretic framework and a beta/binomial hierarchical model to tailor dose-escalation and de-escalation decisions. These rules are conceptually similar to those used by the 3+3 design and all the dose-escalation decisions for a given trial can be pre-calculated under the mTPI design and presented in a two-way table.

The decision rules to “dose escalate” (E), “no change in dose” (S), “dose de-escalate” (D) or “dose de-escalate, unacceptable toxicity” (U) are described below:

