**Table 1. Decision Rules**

Number	Number of Patients treated at a Dose level											
	DLT	n=2	n=3	n=4	n=5	n=6	n=7	n=8	n=9	n=10	n=11	n=12
0	E	E	E	E	E	E	E	E	E	E	E	E
1	D	S	S	S	E	E	E	E	E	E	E	E
2	U	D	D	S	S	S	S	S	S	S	S	S
3		U	U	D	D	S	S	S	S	S	S	S
4			U	U	U	D	D	D	D	D	D	S
5				U	U	U	U	U	D	D	D	D
6					U	U	U	U	U	U	U	D
7						U	U	U	U	U	U	U

Cohorts of patients could receive doses already tested but a dose that is associated with decision “Dose de-escalate, unacceptable toxicity” cannot be revisited and no more patients should be treated at this dose or higher doses for the remainder of the trial.

A minimum of 9 patients treated at the MTD dose is required to establish such dose as the RP2D. The maximum sample size would be N=70 but actual sample size will depend on the underlying dose toxicity profile and variability in actual data realization. The initial dosing regimen tested in Part 1 will be PF-06647263 administered once every 3 weeks (Q3W) consistent with the pre-clinical toxicity study. Evaluation of a weekly (QW) regimen will be initiated when the first patient treated with the Q3W regimen experiences a DLT or Grade 2 thrombocytopenia related to study treatment. The starting dose of the QW regimen will not exceed one-third of the highest Q3W dose evaluated. Once initiated, the 2 regimens will be evaluated in parallel and independently based on the same dose-escalation criteria as described above.

Dose escalation will stop under any of the following conditions:

1. The maximum sample size has been achieved;
2. At least 9 patients have been accumulated at a dose that is predicted to be the MTD;
3. All doses explored appear to be overly toxic and the MTD cannot be determined.

### 2.3. Part 2

Upon identification of the MTD, approximately 30 patients will be enrolled at the MTD in order to explore benefit from treatment as suggested by preclinical findings and will better define the safety profile at the RP2D. This expansion component aims at evaluating ADC (PF-06647263) at the MTD in two cancer indications:

- a. Previously treated metastatic TNBC which expresses EFNA-4 (15 patients).
- b. Advanced epithelial ovarian cancer, primary peritoneal or fallopian tube cancer (OVCA) which expresses EFNA-4 and which has progressed or relapsed during or within 6 months post most recent therapy with a platinum agent (15 patients).

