##### Part 2 (Expansion) Primary Objective

- To confirm safety and tolerability and explore preliminary evidence of anti-tumor activity of PF-06647263 based on response rate (RR) at the RP2D in patients with previously treated metastatic TNBC and advanced platinum-resistant OVCA which express EFNA4.

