#### **4.2. Statistical Decision Rules**

##### **4.2.1. Part 1**

Decision rules are based on calculating unit probability mass (UPM) of three dosing intervals corresponding to under, proper, and over dosing in terms of toxicity. Specifically, the underdosing interval is defined as  $(0; pT - e1)$ , the over-dosing interval  $(pT + e2)$ , and the proper-dosing interval  $(pT - e1, pT + e2)$ , where  $e1$  and  $e2$  are small fractions. For a target DLT rate of 0.25, the target equivalence interval is  $(0.20, 0.30)$ . The three dosing intervals are associated with three different dose-escalation decisions (Table 1). The under-dosing interval corresponds to a dose escalation (E), over-dosing corresponds to a dose de-escalation (D), and proper-dosing corresponds to remaining at the current dose (S). Given a dosing interval and a probability distribution, the unit probability mass (UPM) is defined as the ratio of the probability of the interval to the length of the interval. Once the safety assessment is complete for Cycle 1, the focus will be on allocation of new subjects to the dose most likely to be an MTD.

The study continues accruing until one of the three stopping conditions below is triggered. The algorithm will stop if any of the following criteria is met:

1. The maximum sample size has been achieved.

2. MTD has been identified with sufficient accuracy: at least 9 patients have been accumulated on a dose that is currently estimated to be the MTD, or
3. All doses explored appear to be overly toxic and the MTD cannot be determined.

Specifically the mTPI approach formalizes stopping rules as follow:

Rule 1 (early termination): if the first dose is too toxic  $\rightarrow \Pr(p_1 > p_T / \text{data}) > \xi$  ;  $\xi = 0.975$

Rule 2 (dose exclusion), if dose=  $i$  is too toxic  $\rightarrow \Pr(p_i > p_T / \text{data}) > \xi$  ;  $\xi = 0.975$   
then exclude doses  $\geq i$

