#### **4.2.2. Part 2**

Part 2 of this study is intended to confirm the safety and tolerability of the dose selected in Part 1 while assessing the antitumor activity of PF-06647263 in patients with solid tumors. The DLT rate and analyses of concordance and confidence interval may be estimated.

Analyses may be performed on data from both Part 1 and Part 2 to explore the relationships between PK parameters, safety endpoints, and efficacy endpoints.

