### **5. SAMPLE SIZE DETERMINATION**

Similar to the conventional 3+3 design, the exact sample size of the mTPI design in Part 1 cannot be pre-specified in advance because it is a dynamic feature of the design. The minimum sample size after which the Part 1 can be stopped and MTD declared is 9. If two dose regimens are evaluated, the maximum sample size would be 70 patients.

As for the number of subjects treated at each dose, it is expected that the typical number will be 2-4 subjects for the doses actually studied. For the dose declared as MTD at the end of trial, this number will be at least 9. However, since variable cohort size is allowed, the actual number of subjects treated at each dose will vary from 2 to 12. For example, N=12 is achieved if 4 additional patients are enrolled in a cohort of n=8.

The sample size in Part 2 is based on clinical considerations, rather than statistical justification. It will include 30 subjects in two cohorts of tumor types of interest (ie, TNBC and OVCA) to confirm the safety and tolerability of the recommended dose based on Part 1 and to assess preliminary anti-tumor activity.

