### **7.2.2. MTD Definition**

The MTD would be any doses with true toxicity probabilities in the Equivalence Interval (EI) where the EI is defined as [20%-30%].

In practice, the MTD will be the highest dose associated with the occurrence of DLTs  $\leq 33\%$  (eg, 3/9 evaluable patients experience a DLT during the first treatment cycle).

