### **9.2. Statistical Analyses**

#### **9.2.1. Primary Analysis**

Dose Limiting Toxicity (DLT) is the primary endpoint of the dose escalation component of the study, which will be summarized by dose level using the Per Protocol Analysis Set for patients in the dose escalation portion of the study. A listing of the DLTs will also be provided.

If necessary, a summary and listing of the DLT by malignancy may be provided using the Per Protocol Analysis Set for patients in the MTD expansion portion of the study.

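### Part 2 is meant to confirm safety at the chosen dose, but the SAP commits to no Part 2 DLT rate and offers only an optional split by tumour type

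*SAP*

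**What the plan says.** - **Objective.** SAP section 2.4 opens the Part 2 primary objective with "To confirm safety and tolerability and explore preliminary evidence of anti-tumor activity". Sections 4.2.2 and 5 repeat the safety aim, and section 2.1 allows Part 2 safety data to modify the dose recommended for Phase 2.
- **Primary endpoints.** Section 2.4 names first-cycle DLTs for Part 1 and response rate for Part 2.
- **DLT analysis in Part 2.** Section 9.2.1 has one sentence: "If necessary, a summary and listing of the DLT by malignancy may be provided using the Per Protocol Analysis Set". Section 4.2.2 adds: "The DLT rate and analyses of concordance and confidence interval may be estimated". Neither is a commitment, and section 9.2.1 gives no criterion for when the summary becomes necessary.
- **Analysis set.** Section 6.2 requires at least one baseline and one post-baseline disease assessment for the Per Protocol analysis.
- **How the dose was reached.** Section 2.2 targets a DLT rate of 25% with an equivalence interval of 20-30%, for all solid tumours alike. The text under Table 1 states: "A minimum of 9 patients treated at the MTD dose is required to establish such dose as the RP2D". Section 7.2.2 sets a working limit of 33%, illustrated by "eg, 3/9 evaluable patients experience a DLT during the first treatment cycle".
- **Interval method.** Section 9.1 gives exact two-sided 95% intervals for binary endpoints.
- **Committed safety output.** Section 9.2.3 requires AE and laboratory summaries by worst grade, for Cycle 1 and for later cycles, in the Safety Analysis Set.

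**The concern.** The dose taken into Part 2 is defined by its DLT rate, and Part 1 may measure that rate on as few as 9 patients. Part 2 brings about 30 more patients, whose results played no part in selecting the dose. They are the natural check on it.

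As written, three things can weaken that check:

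1. The Part 2 DLT rate may not be reported at all, because both sentences on it are permissive.
2. If section 9.2.1 is followed, it is reported in two cohorts of 15. That gives up precision for a split the target rate does not call for.
3. It is reported in a set that can exclude the very patients who matter: those who stop early for toxicity before a scan.

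A reader of the study report could then have no direct, reasonably precise estimate of how often the chosen dose produced a DLT in the expansion cohorts.

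**Working it through.** **Inputs.** Part 1: at least 9 patients at the MTD (text under Table 1), and up to 12 at a dose (section 5). Part 2: 15 TNBC plus 15 OVCA, 15 + 15 = 30 (sections 2.1 and 5). Interval: exact, two-sided, 95% (section 9.1). The SAP states no precision for the Part 2 DLT rate, so the event counts below are illustrative. They sit near the 25% target and at the 33% limit, with all patients taken as evaluable.

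**The SAP's own figure.** 3/9 = 33.3%, which agrees with the stated 33%.

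**Formula.** For x events in n patients, the exact (Clopper-Pearson) limits are: lower = the 0.025 quantile of Beta(x, n − x + 1); upper = the 0.975 quantile of Beta(x + 1, n − x).

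| Data | x/n | Rate | Exact 95% CI | Width (points) |
|---|---|---|---|---|
| Part 1, minimum at MTD | 3/9 | 33.3% | 7.5-70.1% | 62.6 |
| Part 1, 12 at MTD | 4/12 | 33.3% | 9.9-65.1% | 55.2 |
| One Part 2 cohort | 4/15 | 26.7% | 7.8-55.1% | 47.3 |
| One Part 2 cohort | 5/15 | 33.3% | 11.8-61.6% | 49.8 |
| Part 2 pooled | 8/30 | 26.7% | 12.3-45.9% | 33.6 |
| Part 2 pooled | 10/30 | 33.3% | 17.3-52.8% | 35.5 |
| Part 1 (9) + Part 2 (30) | 10/39 | 25.6% | 13.0-42.1% | 29.1 |
| Part 1 (9) + Part 2 (30) | 13/39 | 33.3% | 19.1-50.2% | 31.1 |

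**Gain from pooling.** At the same observed rate, pooling the two cohorts narrows the interval by 47.3 − 33.6 = 13.7 points (26.7%) or 49.8 − 35.5 = 14.3 points (33.3%). Adding 9 Part 1 patients at 33.3% narrows it by a further 35.5 − 31.1 = 4.4 points. Most of the gain therefore comes from pooling within Part 2.

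**Effect of the analysis set.** Suppose 8 of 30 patients have a DLT and two of those eight leave before the first scan. All 30 give 8/30 = 26.7%. The Per Protocol set gives 6/28 = 21.4%. The loss runs in one direction when early departure is caused by the DLT.

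**Can the committed AE tables stand in?** Section 9.2.3 tabulates worst grade. Section 7.2.1 defines DLTs partly by duration (Grade 4 neutropenia beyond 7 days), by combination (neutropenia with infection), by delay of the next cycle and by exclusion (infusion-related reactions and similar events). A worst-grade table carries none of these, so a DLT rate cannot be read from it.

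**The case against.** The strongest reply is that the SAP already allows what is asked. Section 4.2.2 mentions a Part 2 DLT rate and confidence interval with no tumour split, section 9.1 supplies the exact method, and section 6.2 allows modified Per Protocol sets drawn from Part 1 or Part 2. This stands in part. A reader might infer that the DLT rate will never be re-estimated after Part 1, and the SAP does not support that. It leaves the re-estimate optional and fixes no pooled form.

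Second, safety is more than DLTs. The Part 2 objective does not name a DLT rate, and the Cycle 1 AE and laboratory tables are committed. So the safety objective is not left unserved. But those tables cannot yield the quantity by which the dose was chosen.

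Third, this is a Phase 1 study with no hypotheses and a Part 2 size set on clinical grounds. That is no bar to the request: section 4.1 puts the emphasis on estimation, and an estimate is all that is asked for.

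Two stronger readings should be set aside:

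- Section 4.2.1 says "MTD has been identified with sufficient accuracy: at least 9 patients have been accumulated on a dose", and a reader might take this as a claim that nine patients show the rate to lie in 20-30%. In context it labels a stopping rule. Even 39 patients would not meet that standard, since 10/39 gives 13.0-42.1%.
- A dose with a true 40% rate gives at most 3 DLTs in 9 with probability 0.48 if the nine are treated as one fixed sample. With cohorts of three kept at the dose to nine patients, no revisits, and no de-escalation under Table 1 along the way, the probability is 0.38. Neither figure is needed for the point made here.

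A fair caution applies to combining the parts. The Part 1 result was used to select the dose, and an exact interval does not remove that selection. Section 7.2.3 also allows an RP2D below the MTD, in which case the nine MTD patients are not at the Part 2 dose.

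**Conclusion.** The point holds as a gap in commitment and a poor default. The SAP sets out to confirm safety at the chosen dose but commits to no Part 2 DLT rate. The one form that section 9.2.1 describes is optional, split into cohorts of about 15, and tied to a set that can lose patients with early DLTs. The split costs about 14 percentage points of interval width at DLT rates of 27-33%: about 47-50 points per cohort against about 34-36 for the 30 pooled.

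These widths rest on illustrative counts, full evaluability and 15 patients per cohort. The 39-patient figures also need the same dose and regimen in both parts, and they ignore dose selection. The size of the Per Protocol effect depends on how many patients leave with a DLT before the first scan, which the SAP cannot tell us. This should be changed, but it does not undermine the design.

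**What to change.** 1. In section 9.2.1, commit to the first-cycle DLT rate at the Part 2 dose with an exact two-sided 95% interval, in all DLT-evaluable Part 2 patients pooled over TNBC and OVCA. Keep the by-malignancy summary as supportive.
2. Define the DLT-evaluable set for this analysis without any condition on tumour assessment.
3. Align section 4.2.2, so that the DLT rate and its interval will be estimated.
4. As a secondary estimate, combine Part 2 with Part 1 patients only where dose and regimen are the same, and state that the Part 1 data were used to select the dose. Posterior probabilities of lying below, within and above 20-30% may be added but are not needed.

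The cost is one table from data already collected, plus a short definition of the set. No dose, schedule or clinical rule changes.

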#### **9.2.2. Secondary Analyses**

##### **9.2.2.1. Efficacy Analysis**

In this Phase 1 study efficacy is a secondary objective. Note that the efficacy analysis is to be conducted by malignancy for patients in the MTD expansion cohorts who are in the Safety Analysis Set and have baseline disease assessment and at least one post-baseline disease assessment. In the event that a large number of patients in the escalation portion of the study have the same malignancy, the efficacy analysis may be conducted.

Summary tables of best Overall Response Rate, Progression Free Survival, and Overall Survival will be provided overall and by malignancy. Efficacy listings will be provided that include best response, first CR/PR date, last date with CR or PR, most recent date without progression, progression date, death date, date of first response and last tumor assessment date, etc.

A response rate overall for Part 1 dose escalation and response rates by low, medium, and high dose groups may be presented.

The following table provides an overview of the efficacy analysis.

Endpoint	Analysis Set	Statistical Method	Model/ Covariates/ Strata	Missing Data	Interpretation
Overall response	Per Protocol, expansion cohorts, etc.	Exact CI	By dose range/ malignancy	Censored per Section 11.3	Secondary Analysis
Progression Free Survival (PFS)	Per Protocol, expansion cohorts	Kaplan-Meier	By malignancy	Censored per Section 11.3	Secondary Analysis
Time to Progression (TTP)	Per Protocol, expansion cohorts	Kaplan-Meier	By malignancy	Censored per Section 11.3	Secondary Analysis
Duration of Response (DR)	Per Protocol, expansion cohorts	Kaplan-Meier	By malignancy	Censored per Section 11.3	Secondary Analysis

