### **3. INTERIM ANALYSES, FINAL ANALYSES AND UNBLINDING**

No interim analysis or blinding is planned for this study. The final analysis will be conducted after the last subject last visit (LSLV).

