## **6.2. 'PER PROTOCOL' Analysis Set**

Part 2: the per protocol (PP) analysis sets includes all enrolled patients (for each indication) who receive at least one dose of study medication and who do not have major treatment deviations during first cycle.

Specifically: Patients with major treatment deviations in Cycle 1 are not evaluable for the RP2D assessment and therefore will not be included in the PP analysis. Major deviations include failure to satisfy major entry criteria (eg, confirmation of the target disease; signed informed consent) or use of other anticancer treatments during the active treatment and disease follow-up phases other than as defined/allowed in this protocol. At least one baseline and one post-baseline disease assessment are required for the PP analysis.

Modified PP analysis sets may be considered for additional analyses and would include patients enrolled either in Part 1 or in Part 2.

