## **6.6. Other Analysis Sets**

### **6.6.1. Modified Intent-to-Treat Set**

The modified intent-to-treat (mITT) is the analysis population that will follow the ITT principle and include subjects receiving at least 1 dose of study medication with baseline assessment and at least 1 post baseline assessment or disease progression or death before the first tumor assessment. The mITT population may be used for interim analysis and conference presentations when the study is still ongoing.

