# 7. ENDPOINTS AND COVARIATES

## 7.1. Efficacy Endpoint(s)

Objective tumor response, as assessed using the Response Evaluation Criteria in Solid Tumor (RECIST) version 1.1 by calculating the Overall Response Rate (ORR), Progression Free Survival (PFS), and Overall Survival (OS).

All efficacy endpoints are secondary in this study, which include objective tumor response, progression-free survival (PFS), and overall survival (OS) for each tumor type in the expansion cohorts. The above efficacy endpoints are derived based on the disease response per investigator evaluation on the CRF pages, which is the primary method of documentation of disease.

- **Overall Response (OR)** – or Response Rate (RR) is defined as complete response (CR) or partial response (PR) according to RECIST 1.1 ([Appendix 2](#)). Overall response is the best response recorded from first dose until disease progression/recurrence.
- **Progression Free Survival (PFS)** - is defined as the time from Cycle 1 Day 1 (C1D1) to first documentation of disease progression or to death due to any cause, whichever occurs first. Subjects last known to be 1) alive 2) on treatment or within the post-treatment follow-up period and 3) progression-free, are censored at the date of the last disease assessment that verified lack of disease progression. Subjects who start new anti-cancer treatment prior to the end of post-treatment follow-up period and have adequate baseline and on-treatment objective disease assessments without evidence of progressive disease are censored at the date of the last objective disease assessment. Subjects with inadequate baseline or no on-study disease assessments are censored at C1D1 unless death occurred prior to the first planned assessment (in which case the death is an event). Subjects with at least one on-study disease assessment who discontinue treatment without disease progression and without death within 28 days of discontinuation are censored at the date of the last objective disease assessment that verified lack of disease progression (if progression or death is within 28 days of discontinuation the progression or death is an event). Subjects with documentation of progression or death after an unacceptably long interval (>16 weeks) since the previous disease assessment will be censored at the time of the previous assessment.

PFS (days) = [progression/death date – C1D1 + 1].

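### The post-baseline assessment condition in SAP Section 9.2.2.1 removes sure non-responders from the response rate and early deaths that the SAP's own PFS rule counts as events

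*SAP*

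**What the plan says.** - **Section 9.2.2.1, text.** Expansion-cohort efficacy is analysed by malignancy in patients "who are in the Safety Analysis Set and have baseline disease assessment and at least one post-baseline disease assessment". The summaries promised there cover response rate, PFS and OS.
- **Section 9.2.2.1, overview table.** The overall-response row gives the analysis set as "Per Protocol, expansion cohorts, etc". The rows for PFS, time to progression (TTP) and duration of response (DR) also name Per Protocol. The missing-data cell of the overall-response row refers to the censoring appendix.
- **Section 6.2.** The Per Protocol set takes treated patients "who do not have major treatment deviations during first cycle" and adds: "At least one baseline and one post-baseline disease assessment are required for the PP analysis".
- **Section 7.1, PFS.** "Subjects with inadequate baseline or no on-study disease assessments are censored at C1D1 unless death occurred prior to the first planned assessment"; such a death is then an event. Appendix 3, Table 3 says the same.
- **Section 6.6.1.** The mITT set keeps treated patients with a baseline and "at least 1 post baseline assessment or disease progression or death before the first tumor assessment". Its use is limited: "The mITT population may be used for interim analysis and conference presentations when the study is still ongoing". Section 3 states: "No interim analysis or blinding is planned for this study".
- **Sections 7.1 and 6.1, OS.** OS runs from the first dose and is assigned to the ITT population, which Section 6.1 equates with everyone enrolled.
- **Status of RR.** Section 2.4 makes RR the Part 2 primary endpoint. Sections 7.1 and 9.2.2.1 call efficacy secondary. Section 4.1 makes estimation the purpose of the final analyses.

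**The concern.** Being assessed after baseline is itself related to outcome. Patients who die, deteriorate or leave before the first scan are the ones most likely to lack an assessment, and none of them can be recorded as a responder. Conditioning on an assessment therefore pushes RR in one direction. For PFS it also conflicts with the SAP's own rules, because the patients those rules are written for are removed before the rules can act.

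Text and table also name different populations for the same endpoints, so an analyst cannot tell which denominator applies. The mITT set shows that early deaths were considered, but no final analysis is assigned to it. What is at stake is the accuracy of the activity estimates in cohorts of about 15, where each dropped patient moves the figure.

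**Working it through.** The SAP gives no RR target, power or precision for Part 2, so there is no planned figure to reproduce.

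**Inputs.** From the SAP: about 15 patients per cohort (Section 2.1) and exact two-sided 95% intervals (Section 9.1). Assumed, because the SAP gives none: responders *x*, treated patients with no post-baseline assessment *e*, and early deaths without an assessment *d*.

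**Step 1: RR under the assessment condition.** All treated, unassessed counted as non-responders: *x*/15. As written: *x*/(15 − *e*). The inflation factor is 15/(15 − *e*), which is 1.07, 1.15, 1.25 and 1.36 for *e* = 1 to 4.

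| *x* | *e*=0 | *e*=1 | *e*=2 | *e*=3 | *e*=4 |
|---|---|---|---|---|---|
| 0 | 0% | 0% | 0% | 0% | 0% |
| 1 | 6.7% | 7.1% | 7.7% | 8.3% | 9.1% |
| 2 | 13.3% | 14.3% | 15.4% | 16.7% | 18.2% |
| 3 | 20.0% | 21.4% | 23.1% | 25.0% | 27.3% |
| 4 | 26.7% | 28.6% | 30.8% | 33.3% | 36.4% |

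Exact 95% intervals for *x* = 3, in order: 4.3–48.1, 4.7–50.8, 5.0–53.8, 5.5–57.2 and 6.0–61.0%. With no responders only the upper limit moves: 21.8, 23.2, 24.7, 26.5 and 28.5%.

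**Step 2: the further Per Protocol exclusions.** These can move RR either way. From 3/15 = 20.0%, dropping one deviating responder gives 2/14 = 14.3%; dropping one deviating non-responder gives 3/14 = 21.4%. Text and table therefore need not give the same RR.

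**Step 3: PFS.** Take *a* assessed patients and *d* unassessed early deaths, with no assessed patient censored before the last early death. If *k* patients are event-free just after that death, the Kaplan-Meier estimate is *k*/(*a* + *d*) for all treated and *k*/*a* for assessed only. The ratio is *a*/(*a* + *d*). From then on both risk sets are the same, so the ratio stays constant. With *a* + *d* = 15:

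| *d* | Ratio | A reported 50% would be |
|---|---|---|
| 0 | 1.00 | 50% |
| 1 | 14/15 = 0.933 | 46.7% |
| 2 | 13/15 = 0.867 | 43.3% |
| 3 | 12/15 = 0.80 | 40.0% |

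Worked case: 12 assessed patients with PFS of 0.75, 0.50 and 0.25 at days 42, 84 and 126.

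- Adding 3 live unassessed patients, censored at C1D1, leaves the curve unchanged.
- Adding 1 early death and 2 live unassessed patients gives 0.692, 0.462 and 0.231 (ratio 12/13).
- Adding 3 early deaths gives 0.60, 0.40 and 0.20 (ratio 12/15).

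**Step 4: limits of the PFS result.** Before the last early death the direction can reverse. With 12 assessed patients, one assessed progression at day 21 and 3 unassessed deaths at day 30, assessed-only PFS at day 21 is 11/12 = 0.917 against 14/15 = 0.933 for all treated. After day 30 it is 0.917 against 0.733, a ratio of 0.80. If that assessed patient is instead censored at day 21, the ratio after day 30 is 11/14 = 0.786, below 0.80. No figure is given for the median, which moves in steps with the scan schedule and may not move. A patient with an unscheduled early scan who then dies stays in the set, so nearly all such deaths are lost, but not strictly all.

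**Step 5: the response row's missing-data rule.** Appendix 3 covers PFS, DR and TTP. Censoring does not say how to classify an unassessed patient in a binary endpoint.

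**The case against.** The strongest objection is that a response-evaluable denominator is a familiar, openly stated choice in a descriptive Phase 1 study. No RR rule in the SAP is broken by it, Sections 7.1 and 9.2.2.1 call efficacy secondary, and the sample size has no statistical basis. The direct contradiction lies only in PFS, and there only for early deaths without an assessment. This limits the weight of the point but does not remove it. Section 2.4 does name RR as the Part 2 primary endpoint, estimation is the stated aim, and the bias from the assessment condition runs one way. The evaluable analysis can stay as supportive.

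The sizes above rest on assumed counts; 4 unassessed of 15 has no support in the SAP. That is correct: they show sensitivity, not expected bias. The RR shifts sit well inside the exact intervals, and the patient accounting in Section 9.2.4 should show who was excluded.

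On OS, the specific ITT statement in Section 7.1 could be read as governing, since the table has no OS row. That reading is possible, but Section 9.2.2.1 lists OS among the summaries under its restriction, so the two places need reconciling.

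Section 6.2 also excludes for failed entry criteria and for other anticancer treatment beyond Cycle 1, so the Per Protocol set departs further from the text's population than the Cycle 1 wording alone suggests. For TTP and DR the lost early deaths do no harm: Table 4 censors them at C1D1, and DR concerns responders only.

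**Conclusion.** The concern holds. Followed as written, Section 9.2.2.1 gives an RR that is never lowered by the assessment condition and is raised whenever a cohort has at least one responder and one unassessed patient. It also gives a PFS curve that omits events required by Section 7.1 and Table 3 and is overstated from the last such death onward.

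Under the assumed counts, each unassessed patient adds roughly 1 to 2 percentage points to an RR of 20% in a cohort of 15. One to three early deaths turn a true 46.7% to 40.0% into a reported 50% PFS, provided no assessed patient is censored before the last of them. If every treated patient is assessed, the assessment condition has no effect. No test decision is involved; the harm is a biased activity estimate and an undetermined analysis set. The mITT set does not repair this, being optional and tied to interim and conference use. This should be fixed before the final analysis.

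**What to change.** In the text and table of Section 9.2.2.1:

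1. Name one population for RR and PFS in each cohort: all treated expansion patients, that is, the Safety Analysis Set without the assessment conditions.
2. In the overall-response row, replace the reference to the censoring appendix with a rule that patients without an evaluable post-baseline assessment count as non-responders.
3. Apply the event and censoring rules of Section 7.1 and Table 3 to PFS as they stand.
4. Keep the Per Protocol or response-evaluable analysis as supportive.
5. Exempt OS from the assessment condition and reconcile its population between Sections 6.1 and 7.1. Because OS starts at the first dose, only treated patients can contribute.

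The cost is SAP wording, with no new data. Compared with the present text rule, RR and later PFS become slightly less favourable, or stay the same if every treated patient is assessed.
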